8.2.8.1.3. Study Drug Interruption or Discontinuation

If a participant develops any one of the following laboratory or clinical changes, interrupt the study-drug and continue close monitoring and comprehensive hepatic evaluation as described in Section 8.2.8.1.1. and 8.2.8.1.2.

ALT or AST ≥3x ULN with hepatic signs/ symptoms ^a or	
ALT or AST ≥5x ULN for more than 2 weeks or	
ALT or AST ≥8x ULN or	
ALT or AST $\geq 3x$ ULN and TBL $\geq 2x$ ULN ^b or INR ≥ 1.5 or	
ALP ≥3x ULN or	
$ALP \ge 2.5x \text{ ULN and TBL} \ge 2x \text{ ULN}^b \text{ or}$	
ALP ≥2.5x ULN with hepatic signs or symptoms ^a	

Examples of hepatic signs or symptoms: severe fatigue, nausea, vomiting, right upper quadrant abdominal pain, fever, rash, and/or eosinophilia >5%.

Interruption or discontinuation of study drug should include the following actions:

- While the participant is not receiving the study drug, clinical and laboratory monitoring should continue at a frequency of 1 to 2 times weekly until liver tests normalize or return to approximate baseline values.
- If the hepatic event continues past the anticipated end of the study (that is, data lock), the investigator should consult with the Lilly-designated medical monitor to determine the need for further data collection beyond the end date of the study (that is, data lock date).
- All the medical information and test results related to close hepatic monitoring and comprehensive hepatic evaluation should be collected and recorded in a hepatic safety CRF.
- Resumption of the study drug after interruption for a hepatic reason can be considered only in consultation with the Lilly designated medical monitor, only if the liver test results returned to near baseline, and if a self-limited non-study-drug etiology is identified. Otherwise, the study drug should be permanently discontinued.

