7.1.2. Hepatic Criteria for Study Drug Interruption or Discontinuation

See Section 8.2.8 for hepatic criteria for study drug interruption or discontinuation.

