8.2.7.1.3. Hypersensitivity

Many drugs, but particularly biologic agents, carry the risk of systemic hypersensitivity reactions. If such a reaction occurs, additional data describing each symptom should be provided to the sponsor in the eCRF.

Sites should have appropriately trained medical staff and appropriate medical equipment available when study participants are receiving the study drug. It is recommended that participants who experience a systemic hypersensitivity reaction be treated per the local standard of care.

If the investigator determines that a systemic hypersensitivity reaction has occurred related to study intervention administration, the participant may be permanently discontinued from the study intervention, and the sponsor's designated medical monitor should be notified. If the investigator is uncertain about whether a systemic hypersensitivity reaction has occurred and whether discontinuation of study intervention is warranted, the investigator may consult the sponsor.

In case of systemic hypersensitivity reactions, defined as anaphylaxis or generalized urticaria, additional blood samples should be collected as described in Appendix 2 (Section 10.2). Laboratory results are provided to the sponsor via the central laboratory.

In the event of drug hypersensitivity reactions (immediate or nonimmediate), up to 3 additional samples will be collected each for PK and immunogenicity at the following time points: as close to the onset of the reaction event as possible, at the resolution of the event if possible, and approximately 30 days following the event.

8.2.8. Hepatic Safety Monitoring, Evaluation, and Criteria for Study Drug Interruption or Discontinuation

This table summarizes actions to take based on abnormal hepatic laboratory or clinical changes.

If this laboratory value is observed	Then		
	Initiate or continue close hepatic monitoring	Initiate comprehensive evaluation	Interrupt or discontinue study drug
ALT or AST ≥3x ULN	X		
ALP ≥2x ULN	X		
TBL ≥2x ULN ^a	X		
ALT or AST ≥5x ULN	X	X	
ALP ≥2.5x ULN	X	X	
ALT or AST ≥3x ULN with hepatic signs or symptoms ^b	X	X	X
ALT or AST ≥5x ULN for more than 2 weeks	X	X	X
ALT or AST ≥8x ULN	X	X	X
ALT or AST ≥3x ULN and TBL ≥2x ULN ^a	X	X	X
ALP ≥3x ULN	X	X	X
ALP ≥2.5x ULN and TBL ≥2x ULN ^a	X	X	X
ALP ≥2.5x ULN with hepatic signs or symptoms ^b	X	X	X

- In participants with Gilbert's syndrome, the threshold for TBL may be higher.

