8.2.8.1.2. Comprehensive Hepatic Monitoring

If a participant develops any one of the following laboratory or clinical changes, initiate a comprehensive hepatic evaluation:

ALT or AST ≥5x ULN or
ALP ≥2.5x ULN or
ALT or AST ≥3x ULN with hepatic signs or symptoms ^a or
ALT or AST ≥5x ULN for more than 2 weeks or
ALT or AST ≥8x ULN or
ALT or AST ≥3x ULN and TBL ≥2x ULN ^b or INR≥ 1.5

- Examples of hepatic signs/symptoms: severe fatigue, nausea, vomiting, right upper quadrant abdominal pain, fever, rash, and/or eosinophilia >5%.
- b In participants with Gilbert's syndrome, the threshold for TBL may be higher.

Comprehensive hepatic evaluation should include the following actions:

- At a minimum, comprehensive hepatic evaluation should include a physical examination and a thorough medical history, as outlined above, as well as tests for PT-INR; tests for viral hepatitis A, B, C, and E; tests for autoimmune hepatitis; and an abdominal imaging study (for example, an ultrasound or CT scan).
- Based on the participant's history and initial results, further testing should be considered in consultation with the Lilly-designated medical monitor, including tests for hepatitis D virus, cytomegalovirus, Epstein-Barr virus, acetaminophen levels, acetaminophen protein adducts, a urine toxicology screen, Wilson's disease, blood alcohol levels, urinary ethyl glucuronide, and blood phosphatidylethanol.
- Based on the circumstances and the investigator's assessment of the participant's clinical condition, the investigator should consider referring the participant for a hepatologist or gastroenterologist consultation, and additional tests, including magnetic resonance cholangiopancreatography, endoscopic retrograde cholangiopancreatography, cardiac echocardiogram, or a liver biopsy.
- Clinical and laboratory monitoring should continue at a frequency of approximately 1 to 2 times weekly until levels normalize or return to approximate baseline values.
- All the medical information and test results related to hepatic monitoring and comprehensive hepatic evaluation should be collected and recorded in a hepatic safety CRF.

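### An INR of 1.5 or more interrupts dosing under Protocol 8.2.8.1.3 but not under the Section 8.2.8 action table, and the and/or grouping of the INR term is undefined

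*Protocol*

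**What the plan says.** Protocol 7.1.2 gives no hepatic criteria of its own. It says only "See Section 8.2.8 for hepatic criteria for study drug interruption or discontinuation".

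Section 8.2.8 opens with an action table, introduced by "This table summarizes actions to take based on abnormal hepatic laboratory or clinical changes". The table has three action columns: close monitoring, comprehensive evaluation, and interruption or discontinuation. Two rows matter here:

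- "ALT or AST ≥3x ULN and TBL ≥2x ULN" is marked in all three columns.
- "ALT or AST ≥5x ULN", without a duration, is marked for monitoring and evaluation; its interruption cell is blank.

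No row or footnote of the table mentions INR.

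Section 8.2.8.1.3 then lists the changes of which any one means the site must "interrupt the study-drug and continue close monitoring and comprehensive hepatic evaluation". On the line combining transaminases with bilirubin, it adds INR of 1.5 or more, joined by a bare *or*. Section 8.2.8.1.2 makes the same addition to its triggers for comprehensive evaluation. It also makes coagulation testing part of the minimum evaluation ("as well as tests for PT-INR").

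**The concern.** This is a stopping threshold in a first-in-human, multicenter study that has no data monitoring committee. Sites need one rule, and the protocol prints two without saying which governs.

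The consequence for a participant can be large. Under 8.2.8.1.3, dosing may resume after a hepatic interruption only in consultation with the medical monitor, and only if liver tests are back near baseline and a self-limited cause other than study drug is found. Otherwise discontinuation is permanent. The same INR result could therefore leave one participant on treatment and end treatment for another, depending on which part of Section 8.2.8 the site used.

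A second problem lies inside the lists. A line of the form *A and B or C* can be read as A with either B or C, or as C alone being enough. Two sites that both work from the list could still act differently.

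**Working it through.** The protocol gives no figure to reproduce here, so the check compares the two rules.

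**Step 1. Interruption criteria side by side**

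| Criterion (multiples of ULN) | Table in 8.2.8 | List in 8.2.8.1.3 |
|---|---|---|
| ALT/AST ≥3 plus hepatic signs or symptoms | interrupt | interrupt |
| ALT/AST ≥5 lasting over 2 weeks | interrupt | interrupt |
| ALT/AST ≥8 | interrupt | interrupt |
| ALT/AST ≥3 plus TBL ≥2 | interrupt | interrupt, **with INR ≥1.5 added as an alternative** |
| ALP ≥3 | interrupt | interrupt |
| ALP ≥2.5 plus TBL ≥2 | interrupt | interrupt |
| ALP ≥2.5 plus hepatic signs or symptoms | interrupt | interrupt |

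Six rows agree exactly; only the fourth differs.

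**Step 2. The rules in logical form**

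Let T be true when any of the seven table rows is met.

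- Table: interrupt if T.
- List, reading 1 (INR counts only with raised transaminases): interrupt if T, or if ALT/AST ≥3 and INR ≥1.5.
- List, reading 2 (INR counts alone): interrupt if T, or if INR ≥1.5.

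Both readings contain T, so the list always interrupts when the table does. The conflict is one-sided. Under reading 1 it occurs when all of these hold:

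- ALT/AST at least 3 and below 8, and not at 5 or above for more than 2 weeks
- TBL below 2
- ALP below 3
- no hepatic signs or symptoms
- INR ≥1.5

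Reading 2 adds participants whose transaminases are below 3.

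**Step 3. A worked profile**

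Take ALT 6 × ULN for less than 2 weeks, TBL 1.5 × ULN, normal ALP, no hepatic signs or symptoms, and INR 1.6.

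- Table: ALT is at least 5, so monitor and evaluate. It is below 8, has not lasted over 2 weeks and comes without symptoms; TBL is below 2 and no ALP row is met. No interruption row applies.
- List, reading 1: 6 ≥ 3 and 1.6 ≥ 1.5, so interrupt.
- List, reading 2: 1.6 ≥ 1.5, so interrupt.

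**Step 4. A grid check**

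The rules were compared over four ALT/AST levels (1, 3.5, 6, 9), four ALP levels (1, 2.2, 2.7, 3.2), two TBL levels (1, 2.5), symptoms yes or no, duration over 2 weeks yes or no, and two INR levels (1, 1.6). That is 4 × 4 × 2 × 2 × 2 × 2 = 256 combinations. Dropping the 2 × 4 × 2 × 2 × 2 = 64 that pair the long duration with ALT/AST below 5 leaves 192.

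| | Reading 1 | Reading 2 |
|---|---|---|
| List interrupts, table does not | 6 | 15 |
| Table interrupts, list does not | 0 | 0 |

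These counts depend on the chosen levels. They show that conflicting profiles exist and are not frequencies.

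**Step 5. Would INR be known?**

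INR is not among the routine safety tests in Appendix 2. It is required in the comprehensive evaluation, which the table itself starts at ALT/AST ≥5 or ALP ≥2.5.

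- Of the 6 conflicting profiles under reading 1, 4 meet one of those entry points: ALT 6 with each of the three ALP levels below 3, and ALT 3.5 with ALP 2.7.
- Under reading 2 there is one more, ALT 1 with ALP 2.7, making 5 of 15.

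That last profile also separates the two readings of the list. With INR 1.6, reading 1 does not interrupt and reading 2 does.

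**The case against.** The strongest reply is that the table is only a summary. A blank cell does not instruct anyone to keep dosing, Section 7.1.2 points to 8.2.8 as a whole, and the two rules are nested, so a site that reads everything would apply the broader trigger. A site that has ordered an INR is probably already working from 8.2.8.1.2, where the INR term is printed immediately before the interruption section. The medical monitor is involved by then, and the investigator may stop treatment on safety grounds anyway. Part A is single-dose, so there is no later dose to withhold.

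Much of this stands as a limit on reach. The conflict needs INR to be the only interruption criterion met, and it matters mainly in Part B (repeat dosing for up to 12 weeks) and Part C (daily dosing). The reply does not remove the defect. The table is presented as the guide to action, reproduces the other six interruption criteria exactly, and does not warn that the list holds more. Nothing gives the list precedence. Reading both parts together does not settle the and/or grouping either, because that ambiguity sits inside the operative lists.

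**Conclusion.** The concern holds. The Section 8.2.8 table and the list in 8.2.8.1.3 give different actions for the same liver result whenever INR is the only interruption criterion met, under either reading of the list. The table also omits INR as a trigger for comprehensive evaluation, which 8.2.8.1.2 includes.

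The affected set is narrow, and the documents give no basis for estimating how often it would arise. The worked profile assumes ALT at 5 × ULN or above for no more than 2 weeks, no hepatic signs or symptoms, and no ALP criterion met; without those conditions the table would interrupt as well. No effect on an endpoint or planned analysis was identified: SAP 10.6.6 cites protocol Section 8.2.8 without separating table from list, and mainly lists the hepatic data. The point should be corrected because it is a stopping rule in a first-in-human study with repeat dosing. It takes no position on which threshold is clinically right.

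**What to change.** Reconcile three places: the Section 8.2.8 table, the list in 8.2.8.1.2 and the list in 8.2.8.1.3. The same criterion should appear in each. If INR is kept, the grouping should be made explicit, with brackets or separate lines, so that it is clear whether INR counts alone or only alongside raised transaminases. A sentence saying which text governs in case of doubt would help. Whether INR belongs in the rule, and at what level, is for the sponsor's clinical team.

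The cost is a text edit to one table row and up to two list lines, plus the amendment and ethics review described in Protocol 10.1.1. Aligning the wording in itself needs no change to the sample size or the SAP analyses.

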8.2.9. Immunological Status Assessments

WBC subpopulations (including, but not limited to, total B cells, total T cells, and NK cells) in blood samples collected at visits and times specified in the SoA (Section 1.3) will be measured using flow cytometry as part of immunophenotyping assessment in Parts A, B, and C. A maximum of 3 samples may be collected at additional time points during the study (as unscheduled samples) if warranted and agreed upon between both the investigator and sponsor. Instructions for the collection and handling of blood samples will be provided by the sponsor. The actual date and 24-hour clock time of each sampling will be recorded. Immunoglobulin samples will also be collected as specified in the SoA (Section 1.3) as part of safety assessment.

8.2.10. Hepatitis B Testing and Monitoring

Testing

Testing for HBV infection includes HBsAg and anti-HBc.

- If HBsAg is positive, the participant is excluded.
- If HBsAg is negative and anti-HBc is negative, the participant is not excluded.

b In participants with Gilbert's syndrome, the threshold for TBL may be higher.

• If HBsAg is negative and anti-HBc is positive, further testing for HBV DNA is required.

- o If the screening HBV DNA is positive, the participant is excluded.
- o If the screening HBV DNA is negative, the participant is not excluded.

Monitoring

If the screening HBV DNA is negative, and proof of HBV vaccination cannot be provided, repeat testing for HBV DNA is required at least every 3 months during the study.

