2.3. Benefit/Risk Assessment

The toxicology data for LY3872386 demonstrate an acceptable nonclinical safety profile and margin of safety to support the transition from preclinical status to a clinical single-dose study in healthy participants and a multiple-dose study in patients with AD.

The nonclinical safety profile of LY3872386 is generally consistent with its intended pharmacology. Primary safety concerns predicted from studies with the ADC and the payload are bacterial and other infections, secondary to decreases in lymphoid tissue lymphocytes and circulating blood lymphocytes. Other potential risks identified for LY3872386 in toxicology studies and consistent with GC pharmacology are

- atrophy of skin hair follicles, especially near SC injection sites, potentially leading to thinning hair or hair loss
- suppression of the HPA axis
- increased serum triglycerides, and
- increased serum glucose.

The safety and efficacy associated with modulation of the IL-4/IL-13/IL-4R axis have been evaluated with approved drugs such as dupilumab and tralokinumab, and the safety and efficacy of GCs as a class are well-established. The key safety concerns and PD effects of LY3872386, including infection, conjunctivitis, hypersensitivity reactions, local injection site reactions, and systemic GC exposure from LY3558533 (free payload), will be closely monitored during the clinical study.

As with other immunomodulatory therapies, LY3872386 and prednisone may increase the risk of developing infections, increase the risk of an infection becoming more serious, and/or change the effectiveness of vaccines administered. LY3872386 may also increase the risk of opportunistic infections and the reactivation of latent infections. Participants will therefore be screened for hepatitis B, hepatitis C, HIV, and TB. In addition, all participants should be monitored for symptoms and signs of infection after administration of LY3872386 or prednisone.

Infusion reactions and hypersensitivity reactions are potential risks for all biologics. These risks will be carefully monitored during the dosing period in Parts A and B (the LY3872386 portions of the study), with close observation after infusion and stopping rules that prevent re-challenge of patients/participants with significant hypersensitivity reactions.

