4.1. Overall Design

Study KMAA is a first-in-human trial designed to characterize the safety and tolerability of LY3872386 as well as the PK of LY3872386, total antibody, and LY3558533 (free payload) in healthy participants and in patients with AD. Additionally, this study will assess the safety, PK, tolerability, and PD of various dose levels of prednisone in healthy participants. The study will enroll participants of any ethnicity. The inclusion of healthy Japanese and Chinese participants in Part A, the LY3872386 SAD portion of this study, will facilitate the inclusion of Japanese and Chinese participants in subsequent clinical trials. The study will be conducted in 3 parts as follows:

- Part A (SAD of LY3872386) will characterize the safety, tolerability, PK, and PD after single IV and SC dose administration of LY3872386 in healthy participants.
- Part B (MAD of LY3872386) will characterize the safety, tolerability, PK, and PD after multiple SC and/or IV dose administrations of LY3872386 in patients with AD.
- Part C CCI will assess the safety, tolerability, PK, and PD after repeat PO administration of prednisone in healthy participants.

Section 1.2 illustrates the study schema and demonstrates the relationship among Parts A, B, and C. Section 1.2 also provides details on dosing and the inclusion of healthy Chinese and Japanese participants. Part A will begin first and will inform and thereby trigger the initiation of Parts B and C.

Screening Period

Screening may occur up to 35 days prior to Day 1 of the study. After obtaining informed consent, participants will be screened for eligibility as detailed in Section 5. Screening procedures will be performed as outlined in the SoA (Section 1.3).

[figure not shown]
Participants who are not enrolled within 35 days of screening may be subjected to an additional medical assessment and/or clinical measurements to confirm their eligibility. The assessments will be repeated at the discretion of the investigator.

Treatment Period and Visit Frequency

Part A: SAD of LY3872386 in Healthy Participants

Part A will be a SAD study of LY3872386 in healthy participants and will be comprised of 8 cohorts. SAD Cohorts 1 to 5 will consist of CCI healthy participants each who will be randomly assigned to receive LY3872386:placebo in a commanner. SAD Cohorts 6 to 8 will consist of CCI participants who will be randomly assigned to receive LY3872386:placebo in a commanner. See Table KMAA.1 for further details.

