 - d. Have used any of the following topical medications within 1 week prior to randomization (Visit 2):
 - topical corticosteroids or topical immune modulators (for example, tacrolimus or pimecrolimus)

Note: pimecrolimus may not be available in all regions, including Japan.

- topical phosphodiesterase type 4 inhibitor, or
- topical Janus kinase inhibitor.

Note: Intranasal or inhaled steroid use is allowed during the trial.

- 46. have received the following excluded medications/treatments within 4 weeks prior to randomization (Visit 2) or plan to use during the study:
 - a. oral systemic corticosteroids and leukotriene inhibitors.
 - b. systemic immunomodulators, including, but not limited to, cyclosporine, methotrexate, mycophenolate mofetil, azathioprine, and Janus kinase inhibitors (such as tofacitinib, ruxolitinib, baricitinib, upadacitinib or abrocitinib).
 - c. sedating antihistamines including, but not limited to, alimemazine, chlorphenamine, clemastine, cyproheptadine, diphenhydramine, hydroxyzine, ketotifen, and promethazine.

Note: Participants may use newer, less sedating antihistamines (for example, fexofenadine, loratadine, and cetirizine).

d. any other systemic therapy used to treat AD or symptoms of AD (approved or off-label use).

- e. phototherapy, including therapeutic phototherapy (psoralen plus ultraviolet-A and ultraviolet-B), excimer laser, or tanning beds.
- 47. patients with a positive beta-D-glucan test at screening and a confirmed diagnosis of pneumocystis pneumonia will be excluded.
- 48. have experienced hypersensitivity to the active substance or to any of the excipients.
- 49. For Japanese participants only: have evidence of, or a positive test for, HBV infection, defined as:
 - a. positive for hepatitis B surface antigen (HBsAg), or
 - b. positive for hepatitis B core antibody (HBcAb) and positive HBV DNA, or
 - c. positive for hepatitis B surface antibody (HBsAb) and positive for HBV DNA.

Note: Patients who are positive for HBcAb or HBsAb and negative for HBV DNA may be enrolled in Part B of the study. In this case, repeat testing for HBV DNA is required at least once every month during the study.

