7.1.5. Serious and Opportunistic Infections Discontinuation and Interruption Criteria

7.1.5.1. Discontinuation: The Following Infections Lead to Study Intervention Discontinuation

HBV or HCV: The participant tests positive for HBV DNA (see Section 8.2.10) or tests positive for HCV RNA (Section 8.2.11).

Note: The HBV DNA result is to be confirmed if initial test result is positive but below the level of quantification (Section 7.1.5.2). Prior to discontinuation of any immunomodulatory and/or immunosuppressive therapy, including study intervention, the participant is to be referred to, evaluated, and managed by a specialist physician with expertise in evaluation and management of viral hepatitis. The timing of discontinuation from study intervention relative to the initiation of any antiviral treatment for hepatitis is to be based on the recommendation of the consulting specialist physician, in conjunction with the investigator, and aligned with medical guidelines and standard of care.

Certain AEs:

- The participant develops HIV infection.
- The participant develops active TB or has untreated LTBI.

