7.1.5.2. Infection-Related Criteria for Temporary Withholding

Temporary withholding of study intervention is required if the participant meets any of the following infection-related criteria during the study:

- Serious or opportunistic infections, as defined in Section 5.2. Study intervention has to be withheld until resolution of all acute clinical signs and symptoms, and completion of all appropriate anti-infective treatment (exception for LTBI, noted below).
- A participant diagnosed with LTBI during the study has to be permanently discontinued from study intervention unless the participant is a candidate for LTBI treatment, and is treated for LTBI as follows:
 - o Study intervention is temporarily withheld for at least the first 4 weeks of LTBI treatment.
 - O After receiving at least 4 weeks of appropriate LTBI therapy (as per World Health Organization or US Centers for Disease Control and Prevention guidelines), if there is no evidence of hepatotoxicity (ALT/AST level must remain ≤2 times ULN) or other treatment intolerance, study intervention may be resumed.
 - The participant must complete appropriate LTBI therapy to remain eligible to receive study intervention.
- HBV DNA results that are reported as positive, or as detecting HBV DNA, but HBV DNA is below the level of quantification. In this situation, the sponsor's designated medical monitor should be contacted regarding the participant's status. HBV DNA testing is to be repeated as soon as it is feasible. If HBV DNA is confirmed as positive, the participant must be permanently discontinued from study intervention.

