Beta D-glucand	FSH ⁱ
Cortisol (serum, cosyntropin stim, and urine)	Thyroid-stimulating hormone (including T3/T4 tests) Syphilis test (including RPR and TPPA as
	appropriate) ^g

Abbreviations: DNA = deoxyribonucleic acid; ED = early discontinuation; FSH = follicle-stimulating hormone; HIV = human immunodeficiency virus; Ig = immunoglobulin; NK cell = natural killer cell; RBC = red blood cell; RPR = Rapid Plasma Regain; TPPA = Treponema Pallidium Particle Agglutination.

Note: Results of these assays will be validated by the local laboratory at the time of testing. Additional tests may be performed or auto calculated by the laboratory as part of its standard panel that cannot be removed. Some of the above parameters are calculated from measured values. The omission of calculated values will not be considered as a protocol violation.

- a To be done centrally. If needed for safety, site may also perform locally.
- b Test only if dipstick result is abnormal.
- ^c Urine drug screen and ethanol breath testing may be repeated prior to admission to the clinical research unit and at other times indicated in the Schedule of Activities. Unscheduled testing is allowed.
- d Evaluation of beta-D-glucan may be performed at a local laboratory. Beta-D-glucan is required at screening for Part B only (to be performed centrally), and if an investigator believes it is warranted, at subsequent visits (may be performed centrally or locally), a beta-D-glucan test may be included in the work up panel at any time during the study. If the beta-D-glucan test is positive, pneumocystis pneumonia (PCP) needs to be ruled out. If PCP is ruled out and the investigator deems the patient fit to continue, the patient may continue in the study. If a patient has a confirmed diagnosis of PCP during the study, the patient must discontinue the study.
- e Not performed at screening.
- f Bedside glucose monitoring is performed using standard glucose monitors and capillary blood taken from fingerstick. Fasting should be approximately 2 hours, at a minimum.
- g Performed at screening only.
- h These tests may be waived if performed within 6 months prior to screening, and if test results are available for "review" for hepatitis B, C, and HIV.
- i To be performed on all female participants.

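### The vaccination clause in Protocol 8.2.10 cancels scheduled HBV DNA retesting only for anti-HBc-positive, DNA-negative participants: 1 to 2 tests lost in non-Japanese Part B

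*Protocol*

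**What the plan says.** Protocol 8.2.10 uses HBsAg and anti-HBc for screening and adds a DNA test in one case: "If HBsAg is negative and anti-HBc is positive, further testing for HBV DNA is required". A positive DNA result excludes the participant; a negative one does not. The monitoring rule then sets two conditions, a negative DNA result at screening and the absence of a vaccination record: "proof of HBV vaccination cannot be provided, repeat testing for HBV DNA is required at least every 3 months during the study". A participant who can show a vaccination record does not meet the second condition.

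Other parts of the protocol bear on this:

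- **5.2.1, criterion 49** is confined to Japanese participants. Its note admits Part B patients who are positive for core or surface antibody and negative for HBV DNA, and says that "repeat testing for HBV DNA is required at least once every month during the study". It makes no exception for vaccination.
- **Appendix 2 (10.2)** marks HBsAg, core antibody and surface antibody with footnote g, "Performed at screening only". HBV DNA does not carry that footnote. It carries footnote h, under which a test done in the 6 months before screening can stand in.
- **2.3** states that "LY3872386 may also increase the risk of opportunistic infections and the reactivation of latent infections".
- **7.1.5.1** discontinues study intervention if "The participant tests positive for HBV DNA". **7.1.5.2** withholds it when DNA is detected below the level of quantification, and adds: "If HBV DNA is confirmed as positive, the participant must be permanently discontinued from study intervention".

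The SAP adds no rule on HBV retesting.

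**The concern.** The DNA test exists in 8.2.10 because of a positive anti-HBc result, and it is ordered whatever the vaccination history. The next rule then lets vaccination history decide whether the test is ever repeated. Neither document says why a vaccination record should outweigh the anti-HBc result at that stage when it did not at screening.

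At stake is whether the HBV stopping and withholding rules can be triggered at all by a planned test. They act on HBV DNA alone, with no liver-enzyme condition. For an exempted participant, 8.2.10 requires no further DNA test. Two Part B patients with the same serology and the same vaccination record would be treated differently: monthly DNA if Japanese, no required retest otherwise.

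The practical consequence is largest in Part B, the only part where a retest falling due under this rule could still stop a dose of LY3872386. In Part A the single dose has already been given, so a positive retest would serve detection and referral only.

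**Working it through.** **Step 1. Whom can the clause reach?** Following 8.2.10 branch by branch:

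| HBsAg | anti-HBc | Screening DNA | Vaccination record | Result |
|---|---|---|---|---|
| positive | any | – | any | excluded |
| negative | negative | not ordered | any | enrolled; monitoring rule not triggered |
| negative | positive | positive | any | excluded |
| negative | positive | negative | none | enrolled; retested |
| negative | positive | negative | yes | enrolled; **not retested** |

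The record changes the outcome only between the last two rows. Every exempted participant under 8.2.10 is therefore anti-HBc-positive and DNA-negative.

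**Step 2. Length of Part B.** Treatment lasts 12 weeks and follow-up 14 weeks after the last dose (4.1).

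- Last dose: 1 + 7 × 12 = Day 85, which matches the Day 85 PK profile in SAP 10.3.1.
- Final visit: 1 + 7 × (12 + 14) = Day 183, which matches Day 183 ± 3 in the Amendment b summary of changes.

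**Step 3. Retests that would fall due in Part B.** The documents state no count. Assumptions: 3 months = 91 days, and the screening sample is taken *s* days before Day 1, with *s* from 1 to 35, since "Screening may occur up to 35 days prior to Day 1 of the study". Retest *k* is due on Day 1 + 91*k* − *s*; setting *s* = 0 counts from Day 1.

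| Counted from | 1st due | 2nd due | 3rd due | Due by final visit (Day 180–186) |
|---|---|---|---|---|
| Screening, *s* = 35 | Day 57 | Day 148 | Day 239 | 2 |
| Screening, *s* = 7 | Day 85 | Day 176 | Day 267 | 2 |
| Screening, *s* = 1 | Day 91 | Day 182 | Day 273 | 1 if the visit is before Day 182, otherwise 2 |
| Day 1 | Day 92 | Day 183 | Day 274 | 1 if the visit is before Day 183, otherwise 2 |

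Intervals of 84, 90 and 91.3 days, checked for screening at 35 and 7 days and for Day 1, also give 1 or 2. An exempted participant loses these tests and has no DNA test required by 8.2.10 for 183 − 1 = 182 days from Day 1, or up to 182 + 35 = 217 days from screening. The gap is longer if an older result was accepted under footnote h.

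**Step 4. Other groups.**

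- Part A: final visit 1 + 7 × 12 = Day 85. The first retest is due on Day 57 to 91 (from screening) or Day 92 (from Day 1), so 0 to 1 is lost.
- Part C, longest group: 30 + 14 = Day 44, at latest Day 48 with the ± 4-day window. The earliest due day is 57, so 0 is lost.
- Japanese Part B: 0 lost. Criterion 49 gives about 5 to 7 tests by Day 183, depending on the start point and on whether a month is 28 or 30.4 days.

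**The case against.** **Other tests could pick up reactivation.** This stands in part. Chemistry is drawn at every Part B visit in schedule 1.3.2.1 and at most in 1.3.2.2. Close hepatic monitoring (8.2.8.1.1) points to Appendix 6, which lists HBV tests; comprehensive evaluation (8.2.8.1.2) includes hepatitis B; and Appendix 2 lets the investigator add tests. A reader might infer that an exempted participant can have no HBV test on study, and that would be wrong. These routes need a liver abnormality or a clinical judgment first, however, whereas the 7.1.5 rules act on DNA alone. The documents do not show which would act sooner.

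**Absence is hard to prove in a redacted document.** This also stands. Footnote g is not attached to HBV DNA, so Appendix 2 does not make that assay screening-only. The Schedule of Activities comments and several rows are blacked out. The text of 8.2.10 itself is legible, and the exemption is in it.

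**Calling the exemption wrong needs virology from outside the documents.** It would, if the point were that vaccination is clinically irrelevant. The point here is narrower: the exemption is out of step with the protocol's own risk statement, stopping rules and criterion 49.

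**A tempting stronger reading** is that the 3-month interval has no start date, so that even non-exempt patients would be retested only after the last dose, at about Day 92. The documents do not support that as an error. Repeating a screening test implies counting from screening, and the rule sets a maximum interval, so a draw at or before Visit 8 complies. Day 92 is only the latest day under one assumed start point and a 91-day interval.

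**Conclusion.** The point holds for the vaccination clause. Within 8.2.10 it takes scheduled HBV DNA retesting away only from anti-HBc-positive, DNA-negative participants. The loss is 1 to 2 tests in non-Japanese Part B, 0 to 1 in Part A, and none in Part C or in Japanese Part B.

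This rests on two readings. A quarter is taken as 84 to 91.3 days. The note under criterion 49 is taken to apply to Japanese patients only, as its heading says; if it covered all of Part B, no Part B tests would be lost, but it would then contradict 8.2.10.

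How many participants are affected cannot be worked out: the Part B sample size is redacted, and no anti-HBc prevalence or vaccination rate is given. It may be none. No harm has been shown, and no statistical analysis changes. The case for acting is that the gap sits in the monitoring rule for a risk the protocol names, and that closing it is cheap.

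**What to change.** Delete the vaccination condition from the monitoring rule in 8.2.10. Suggested wording:

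*If anti-HBc is positive and the screening HBV DNA is negative, HBV DNA is tested again at intervals of no more than 3 months for the rest of the study, whatever the vaccination history. Japanese Part B patients follow the monthly rule in exclusion criterion 49.*

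Optional clarification, not the correction of an error: count the interval from the most recent HBV DNA test, or from the screening visit if that test was waived under Appendix 2 footnote h; and in Part B draw the first repeat at an existing visit before the last dose at Visit 8.

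Cost: one sentence at the next amendment, and about 1 to 2 extra HBV DNA assays per affected Part B patient (at most 1 in Part A). The assay is already listed in Appendix 2 and can be drawn at existing visits. The core change leaves the rule for participants without a vaccination record as it is.
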